## Dissemination of Clinical Study Data

- Where required by applicable regulatory requirements, an investigator signatory will be identified for the approval of the clinical study report. The investigator will be provided reasonable access to statistical tables, figures, and relevant reports and will have the opportunity to review the complete study results at a GSK site or other mutually-agreeable location.
- GSK will also provide the investigator with the full summary of the study results. The investigator is encouraged to share the summary results with the study participants, as appropriate.
- The procedures and timing for public disclosure of the results summary and for development of a manuscript for publication will be in accordance with GSK Policy.

## Data Quality Assurance

- All participant data relating to the study will be recorded on printed or electronic CRF unless transmitted to the sponsor or designee electronically (eg, laboratory data). The investigator is responsible for verifying that data entries are accurate and correct by physically or electronically signing the CRF.
- The investigator must maintain accurate documentation (source data) that supports the information entered in the CRF.
- The investigator must permit study-related monitoring, audits, IRB/IEC review, and regulatory agency inspections and provide direct access to source data documents.
- The sponsor or designee is responsible for the data management of this study including quality checking of the data.
- Study monitors will perform ongoing source data verification to confirm that data entered into the CRF by authorized site personnel are accurate, complete, and verifiable from source documents; that the safety and rights of participants are being protected; and that the study is being conducted in accordance with the currently approved protocol and any other study agreements, ICH GCP, and all applicable regulatory requirements.
- Records and documents, including signed ICF, pertaining to the conduct of this study must be retained by the investigator for 25 years from the issue of the final Clinical Pharmacology Study Report (CPSR)/ equivalent summary unless local regulations or institutional policies require a longer retention period. No records may be destroyed during the retention period without the written approval of the sponsor. No records may be transferred to another location or party without written notification to the sponsor.

## Source Documents

- Source documents provide evidence for the existence of the participant and substantiate the integrity of the data collected. Source documents are filed at the investigator's site.
- Data reported on the CRF or entered in the eCRF that are transcribed from source documents must be consistent with the source documents or the discrepancies must be explained. The investigator may need to request previous medical records or transfer records, depending on the study. Also, current medical records must be available.
- Definition of what constitutes source data can be found in the SRM.

## Study and Site Closure

GSK or its designee reserves the right to close the study site or terminate the study at any time for any reason at the sole discretion of GSK. Study sites will be closed upon study completion. A study site is considered closed when all required documents and study supplies have been collected and a study-site closure visit has been performed.

The investigator may initiate study-site closure at any time, provided there is reasonable cause and sufficient notice is given in advance of the intended termination.

Reasons for the early closure of a study site by the sponsor or investigator may include but are not limited to:

- Failure of the investigator to comply with the protocol, the requirements of the IRB/IEC or local health authorities, the sponsor's procedures, or GCP guidelines
- Inadequate recruitment of participants by the investigator
- Discontinuation of further study treatment development

## 12.5. Appendix 5: Adverse Events: Definitions and Procedures for Recording, Evaluating, Follow-up, and Reporting

### Definition of AE

#### AE Definition

- An AE is any untoward medical occurrence in a clinical study participant, temporally associated with the use of a study treatment, whether or not considered related to the study treatment.
- NOTE: An AE can therefore be any unfavorable and unintended sign (including an abnormal laboratory finding), symptom, or disease (new or exacerbated) temporally associated with the use of a study treatment.

#### Events Meeting the AE Definition

- Any abnormal laboratory test results (hematology, clinical chemistry, or urinalysis) or other safety assessments (eg, ECG, radiological scans, vital signs measurements), including those that worsen from baseline, considered clinically significant in the medical and scientific judgment of the investigator (ie, not related to progression of underlying disease).
- Exacerbation of a chronic or intermittent pre-existing condition including either an increase in frequency and/or intensity of the condition.
- New conditions detected or diagnosed after study treatment administration even though it may have been present before the start of the study.
- Signs, symptoms, or the clinical sequelae of a suspected drug-drug interaction.
- Signs, symptoms, or the clinical sequelae of a suspected overdose of either study treatment or a concomitant medication. Overdose per se will not be reported as an AE/SAE unless it is an intentional overdose taken with possible suicidal/self-harming intent. Such overdoses should be reported regardless of sequelae.

#### Events NOT Meeting the AE Definition

- Any clinically significant abnormal laboratory findings or other abnormal safety assessments which are associated with the underlying disease, unless judged by the investigator to be more severe than expected for the participant's condition.
- The disease/disorder being studied or expected progression, signs, or symptoms of the disease/disorder being studied, unless more severe than expected for the participant's condition.
- Medical or surgical procedure (eg, endoscopy, appendectomy): the condition that leads to the procedure is the AE.
- Situations in which an untoward medical occurrence did not occur (social and/or

convenience admission to a hospital).

- Anticipated day-to-day fluctuations of pre-existing disease(s) or condition(s) present or detected at the start of the study that do not worsen.

## Definition of SAE

If an event is not an AE per definition above, then it cannot be an SAE even if serious conditions are met (eg, hospitalization for signs/symptoms of the disease under study, death due to progression of disease).

**A SAE is defined as any untoward medical occurrence that, at any dose:**

### a. Results in death

### b. Is life-threatening

The term 'life-threatening' in the definition of 'serious' refers to an event in which the participant was at risk of death at the time of the event. It does not refer to an event, which hypothetically might have caused death, if it were more severe.

### c. Requires inpatient hospitalization or prolongation of existing hospitalization

In general, hospitalization signifies that the participant has been detained (usually involving at least an overnight stay) at the hospital or emergency ward for observation and/or treatment that would not have been appropriate in the physician's office or outpatient setting. Complications that occur during hospitalization are AE. If a complication prolongs hospitalization or fulfills any other serious criteria, the event is serious. When in doubt as to whether "hospitalization" occurred or was necessary, the AE should be considered serious.

Hospitalization for elective treatment of a pre-existing condition that did not worsen from baseline is not considered an AE.

### d. Results in persistent disability/incapacity

- The term disability means a substantial disruption of a person's ability to conduct normal life functions.
- This definition is not intended to include experiences of relatively minor medical significance such as uncomplicated headache, nausea, vomiting, diarrhea, influenza, and accidental trauma (eg, sprained ankle) which may interfere with or prevent everyday life functions but do not constitute a substantial disruption.

### e. Is a congenital anomaly/birth defect

### f. Other situations:

- Medical or scientific judgment should be exercised in deciding whether SAE reporting is appropriate in other situations such as important medical events that may not be immediately life-threatening or result in death or hospitalization but may

jeopardize the participant or may require medical or surgical intervention to prevent one of the other outcomes listed in the above definition. These events should usually be considered serious.

Examples of such events include invasive or malignant cancers, intensive treatment in an emergency room or at home for allergic bronchospasm, blood dyscrasias or convulsions that do not result in hospitalization, or development of drug dependency or drug abuse.

## Recording AE and SAE

### AE and SAE Recording

- When an AE/SAE occurs, it is the responsibility of the investigator to review all documentation (eg, hospital progress notes, laboratory, and diagnostics reports) related to the event.
- The investigator will then record all relevant AE/SAE information in the CRF.
- It is **not** acceptable for the investigator to send photocopies of the participant's medical records to GSK in lieu of completion of the GSK /AE/SAE CRF page.
- There may be instances when copies of medical records for certain cases are requested by GSK. In this case, all participant identifiers, with the exception of the participant number, will be redacted on the copies of the medical records before submission to GSK.
- The investigator will attempt to establish a diagnosis of the event based on signs, symptoms, and/or other clinical information. Whenever possible, the diagnosis (not the individual signs/symptoms) will be documented as the AE/SAE.

### Assessment of Intensity

The investigator will make an assessment of intensity for each AE and SAE reported during the study and assign it to 1 of the following categories:

- **Mild:** An event that is easily tolerated by the participant, causing minimal discomfort and not interfering with everyday activities.
- **Moderate:** An event that causes sufficiently discomfort and interferes with normal everyday activities.
- **Severe:** An event that prevents normal everyday activities. An AE that is assessed as severe should not be confused with an SAE. Severe is a category utilized for rating the intensity of an event; and both AE and SAE can be assessed as severe.

An event is defined as 'serious' when it meets at least 1 of the predefined outcomes as described in the definition of an SAE, NOT when it is rated as severe.

**Assessment of Causality**

- The investigator is obligated to assess the relationship between study treatment and each occurrence of each AE/SAE.
- A "reasonable possibility" of a relationship conveys that there are facts, evidence, and/or arguments to suggest a causal relationship, rather than a relationship cannot be ruled out.
- The investigator will use clinical judgment to determine the relationship.
- Alternative causes, such as underlying disease(s), concomitant therapy, and other risk factors, as well as the temporal relationship of the event to study treatment administration will be considered and investigated.
- The investigator will also consult the Investigator's Brochure (IB) and/or Product Information, for marketed products, in his/her assessment.
- For each AE/SAE, the investigator **must** document in the medical notes that he/she has reviewed the AE/SAE and has provided an assessment of causality.
- There may be situations in which an SAE has occurred and the investigator has minimal information to include in the initial report to GSK. However, **it is very important that the investigator always make an assessment of causality for every event before the initial transmission of the SAE data to GSK.**
- The investigator may change his/her opinion of causality in light of follow-up information and send an SAE follow-up report with the updated causality assessment.
- The causality assessment is one of the criteria used when determining regulatory reporting requirements.

**Follow-up of AE and SAE**

- The investigator is obligated to perform or arrange for the conduct of supplemental measurements and/or evaluations as medically indicated or as requested by GSK to elucidate the nature and/or causality of the AE or SAE as fully as possible. This may include additional laboratory tests or investigations, histopathological examinations, or consultation with other health care professionals.
- If a participant dies during participation in the study or during a recognized follow-up period, the investigator will provide GSK with a copy of any post-mortem findings including histopathology.
- New or updated information will be recorded in the originally completed CRF.
- The investigator will submit any updated SAE data to GSK within 24 h of receipt of the information.

## Reporting of SAE to GSK

### SAE Reporting to GSK via Electronic Data Collection Tool

- The primary mechanism for reporting SAE to GSK will be the electronic data collection tool.
- If the electronic system is unavailable, then the site will use the paper SAE data collection tool (see next section) in order to report the event within 24 h.
- The site will enter the SAE data into the electronic system as soon as it becomes available.
- The investigator or medically-qualified sub-investigator must show evidence within the eCRF (e.g., check review box, signature, etc.) of review and verification of the relationship of each SAE to IP/study participation (causality) within 72 h of SAE entry into the eCRF.
- After the study is completed at a given site, the electronic data collection tool will be taken off-line to prevent the entry of new data or changes to existing data.
- If a site receives a report of a new SAE from a study participant or receives updated data on a previously reported SAE after the electronic data collection tool has been taken off-line, then the site can report this information on a paper SAE form (see next section) or to the Medical Monitor by telephone.
- Contacts for SAE reporting can be found in the SRM.

### SAE Reporting to GSK via Paper CRF

- Facsimile transmission of the SAE paper CRF is the preferred method to transmit this information to the Medical Monitor.
- In rare circumstances and in the absence of facsimile equipment, notification by telephone is acceptable with a copy of the SAE data collection tool sent by overnight mail or courier service.
- Initial notification via telephone does not replace the need for the investigator to complete and sign the SAE CRF pages within the designated reporting time frames.
- Contacts for SAE reporting can be found in the SRM.

## 12.6. Appendix 6: Contraceptive Guidance and Collection of Pregnancy Information

### Definitions

#### Woman of Childbearing Potential (WOCBP)

A woman is considered fertile following menarche and until becoming post-menopausal unless permanently sterile (see below).

#### Women in the following categories are not considered WOCBP

1. Premenarchal
2. Premenopausal female with ONE of the following:
  - Documented hysterectomy
  - Documented bilateral salpingectomy
  - Documented bilateral oophorectomy

Note: Documentation can come from the site personnel's: review of participant's medical records, medical examination, or medical history interview.

3. Postmenopausal female
  - A postmenopausal state is defined as no menses for 12 months without an alternative medical cause. A high follicle stimulating hormone (FSH) level in the postmenopausal range is to be used to confirm a postmenopausal state in women not using hormonal contraception or hormonal replacement therapy (HRT). However, in the absence of 12 months of amenorrhea, a single FSH measurement is insufficient.
  - Females on HRT and whose menopausal status is in doubt will be required to use one of the non-hormonal highly effective contraception methods if they wish to continue their HRT during the study. Otherwise, they must discontinue HRT to allow confirmation of postmenopausal status before study enrollment.

### Contraception Guidance

#### Female participants

Female participants of childbearing potential that are **not** currently utilizing a highly-effective contraceptive method are eligible to participate if a pregnancy test conducted on or between Day -7 to Day -4 and again pre-dose (Day -1 or Day 0) is negative. It is not necessary to require participants to start a new contraceptive method if they are not already established on one.

Female participants of childbearing potential that are currently utilizing a highly-effective contraceptive method are eligible to participate if they agree to continue to use this method consistently and correctly as described in [Table 6](#). In this instance a negative

pregnancy test on or between Day -7 to Day -4 and again pre-dose (Day -1 or Day 0) would not be required.

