## 2. SCHEDULE OF ACTIVITIES (SOA)

Procedure	Screening 	Day -1	Pre-Dose	0 h	0.5 h	1 h	1.5 h	2 h	3 h	4 h	6 h	8 h	10 h	12 h	24 h	36 h	48 h	Follow-up 
Informed Consent	X																	
Inclusion & Exclusion Criteria	X	X																
Demography	X																	
Full physical exam	X																	
Medical history	X																	
Past/current medications	X																	
Laboratory assessments 	X																X	X
Drug/Alcohol Screen	X	X																
12-lead ECG	X	X															X	X
Vital Signs and Weight	X	X															X	X
Pregnancy Test	X 	X 																
Females only: Estrogen and FSH 	X																	

Procedure	Screening 	Day -1	Pre-Dose	0 h	0.5 h	1 h	1.5 h	2 h	3 h	4 h	6 h	8 h	10 h	12 h	24 h	36 h	48 h	Follow-up 
Admission to Unit		X																
Brief Physical Exam		X															X	X
Administration of daprodustat				X														
PK blood sampling			X		X	X	X	X	X	X	X	X	X	X	X	X	X	
Protein binding sample			X						X					X	X			
EPO blood sampling			X		X	X	X	X	X	X	X	X	X	X	X	X	X	
Adverse Events Assessment	X	X	X	X	X	X	X	X	X	X	X	X	X	X	X	X	X	X
Review Concomitant Medications		X	X												X		X	X
Discharge from Unit																	X	

 All participants will undergo screening assessments within 28 days of enrolment.

 A follow-up visit will occur 10-14 days after the dose of study treatment.

 Laboratory assessment guidance can be found in [Appendix 3](#).

 For women of childbearing potential that are not using an approved method of contraception (see [Appendix 6](#)), one negative pregnancy test between Day -7 and Day -4 AND another negative pregnancy test on Day -1 is required. Additional guidance can be found in Section 9.5.5.

 All females are to have estrogen and FSH measured at screening.

- The timing and number of planned study assessments, including safety, pharmacokinetic and pharmacodynamic assessments may be altered during the course of the study based on newly available data (e.g., to obtain data closer to the time of peak plasma concentrations) to ensure appropriate monitoring.

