#### 6.1.1. Inclusion Criteria for All Participants

AGE
1. Participant must be at least 18 years of age inclusive, at the time of signing the informed consent.
MEDICAL CONDITIONS
2. Hemoglobin values at screening $\leq 16.0$ g/dL for males and $\leq 14.0$ g/dL for females.
WEIGHT
3. Body weight $\geq 45$ kg and body mass index (BMI) within the range 18-40 kg/m  (inclusive).
SEX
4. Male or female Female participants: A female participant is eligible to participate if she is not breastfeeding, and at least one of the following applies: (i) Not pregnant as confirmed by two pregnancy tests (see Section 9.5.5) (ii) Not a woman of childbearing potential (WOCBP) as defined in Appendix 6 (iii) For WOCBP that are currently utilizing a highly-effective contraceptive method prior to enrolment, agrees to follow the contraceptive guidance in Appendix 6 during the treatment period to the follow-up visit. (Additional guidance can be found in Section 9.5.5.)
INFORMED CONSENT
5. Capable of giving signed informed consent which includes compliance with the requirements and restrictions listed in the informed consent form (ICF) and in this

protocol.
-----------

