### 9.5.5. Pregnancy Testing

In this study, participants will have a drug exposure duration of <5 days including dosing plus 5 half-lives and dosing will occur in an inpatient setting. Given this scenario, pregnancy risks are effectively mitigated by adequately ruling out pregnancy at the time of dosing. Thus, it is not necessary to require participants to start a new contraceptive method if they are not already established on one. To ensure capture of women of childbearing potential in this category who may have conceived but are just shy of being able to identify the pregnancy with current detection methods, it is recommended that two pregnancy tests are done in a short time span.

Therefore, for WOCBP that are **not** currently utilizing a highly-effective contraceptive method listed in [Appendix 6](#), a negative pregnancy test on or between Day -7 to Day -4 and again pre-dose (Day -1 or Day 0) is required. WOCBP who are already using a highly effective contraceptive method listed in [Appendix 6](#) (<1% failure rate per year when used consistently and correctly) should continue this method until the follow-up visit at a minimum. In this case, a negative screening test within 28 days of dosing and again pre-dose (Day -1 to Day 0) is sufficient and the additional Day -7 to -4 test is not needed.

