**Pregnancy Testing**

- WOCBP should only be included after a confirmed menstrual period and a negative highly sensitive urine pregnancy test at the times listed in the SoA (Section 2)

- Additional pregnancy testing is not required during the treatment period and at 48 h after the last dose of study treatment
- Pregnancy testing will be performed whenever a menstrual cycle is missed or when pregnancy is otherwise suspected
- Pregnancy testing, with a sensitivity of 2 mIU/mL will be performed using the test kit provided by the central laboratory.

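### Appendix 6 waives the pre-dose pregnancy test that Section 9.5.5 expects for women already on highly effective contraception

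*Protocol*

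**What the plan says.** All references are to the current protocol (Amendment 1).

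- **Section 9.5.5, Pregnancy Testing**, for women of childbearing potential (WOCBP) already on a highly effective method: "In this case, a negative screening test within 28 days of dosing and again pre-dose (Day -1 to Day 0) is sufficient". The sentence ends by dropping only the extra test in the week before dosing. The section's reasoning is that "pregnancy risks are effectively mitigated by adequately ruling out pregnancy at the time of dosing".
- **Appendix 6 (Section 12.6), Contraception Guidance**, for the same women: "Female participants of childbearing potential that are currently utilizing a highly-effective contraceptive method are eligible to participate if they agree to continue to use" that method. The paragraph closes by saying that a negative "pregnancy test on or between Day -7 to Day -4 and again pre-dose (Day -1 or Day 0) would not be required".
- **Appendix 6, Pregnancy Testing**: WOCBP should be included only after a confirmed menstrual period and "a negative highly sensitive urine pregnancy test at the times listed in the SoA (Section 2". No exemption for contraceptive users is given.
- **Section 6.1.1, inclusion criterion 4(iii)**: a WOCBP on a highly effective method qualifies if she "agrees to follow the contraceptive guidance in Appendix 6 during the treatment period to the follow-up visit". The criterion names no test for her and adds a pointer to Section 9.5.5.
- **Section 2, Schedule of Activities**: the pregnancy-test row is marked at Screening and Day -1, but both marks carry footnote 4, which covers only WOCBP not using an approved method. It says "another negative pregnancy test on Day -1 is required. Additional guidance can be found in Section 9.5.5".

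**The concern.** The two sections address the same women and disagree on whether they are tested before the dose. A site that follows the Appendix 6 paragraph could give an investigational drug to a woman without a pregnancy test at the time of dosing, although Section 9.5.5 builds its risk control on that test. Sites reading different sections could also act differently. Section 9 allows no protocol waivers and treats adherence to the schedule as mandatory, so either practice could be recorded as a deviation from the other section.

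**Working it through.** The main check is a comparison of text; the arithmetic serves only to size the risk.

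**Step 1. Tests called for in a WOCBP already on a highly effective method**

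| Source | Screening | Day -7 to -4 | Pre-dose |
|---|---|---|---|
| Section 9.5.5 | Yes, within 28 days of dosing | No | Yes, Day -1 to Day 0 |
| Appendix 6, Contraception Guidance | Not mentioned | No | No |
| Appendix 6, Pregnancy Testing | Yes, as a schedule time | Not listed as a schedule column | Yes, as a schedule time (Day -1) |
| Schedule footnote 4 | No rule for users; refers to 9.5.5 | No rule for users | No rule for users |
| Inclusion criterion 4(iii) | No test named; refers to Appendix 6 and 9.5.5 | No test named | No test named |

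One place waives the pre-dose test, two call for it, and two are silent and refer onward. Appendix 6 is on both sides.

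**Step 2. Can a site reach the waiver from the eligibility criteria?** Criterion 4 needs only one of its three limbs to apply. Limb (i) requires two negative tests; limb (iii) requires none and directs the woman to the Appendix 6 guidance, where the waiver stands. The reference to Section 9.5.5 is offered as additional guidance and does not say which section governs.

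**Step 3. Is it new?** No. The original protocol has the same conflict between the same two sections. The Amendment 1 summary of changes lists no change to either, and both were carried forward.

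**Step 4. Size**

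- Participants (Section 5.1, Table 1): Part 1 has 2 × 8 = 16. With Part 2, which is conditional, 4 × 8 = 32. The number of WOCBP on contraception is not stated and could be zero.
- Longest gap between a screening test and dosing (Section 9.5.5): 28 days.
- Failure rate with consistent and correct use (Section 9.5.5; Appendix 6, Table 6): under 1% a year.
- Chance of conception in the gap, per woman: below 0.01 × 28/365 = 0.00077, or about 0.08%.

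The last figure assumes a negative screening test and correct use. The Appendix 6 paragraph does not ask for the screening test. Table 6, note 1, says that typical-use failure rates may differ, but gives none. The result scales in proportion: each further 1% a year in the failure rate adds about 0.08 percentage points.

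**The case against.** The strongest reply is that the Appendix 6 sentence repeats, word for word, the pair of tests set for non-users in the paragraph above it. It may be meant only to lift that paired schedule, leaving Section 9.5.5 to supply the schedule for users. Most routes do lead there: it is the dedicated testing section, footnote 4 and criterion 4 both refer to it, the schedule row marks Screening and Day -1, and the testing bullets in Appendix 6 itself ask for a negative test at those times. Criterion 4(iii) can also be read as concerning continued contraception after dosing. Section 9.5.5 calls its two tests sufficient rather than required, and its rationale mainly explains why non-users need not start contraception. The absolute risk is tiny.

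Much of this stands as mitigation. The paired reading may be what was intended, and a site reading the whole protocol would probably test. But the sentence names the pre-dose test as not required, nothing in that paragraph restores it, and footnote 4 leaves users out. Calling two tests sufficient sets the minimum accepted in place of the fuller sequence, and the closing clause of that rule, "again pre-dose (Day -1 to Day 0) is sufficient and the additional Day -7 to -4 test is not needed", releases one test only. A check before dosing should not depend on a charitable reading.

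**Conclusion.** The concern holds. As written, the Appendix 6 Contraception Guidance states a rule for contraceptive users that contradicts Section 9.5.5 and the testing bullets in the same appendix, and following it would allow dosing without a pre-dose pregnancy test. This is a participant-safety and consistency error that should be corrected.

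The effect is small: few women, a single dose, and a conception risk below about 0.08% per woman, provided she had a negative screening test within 28 days and uses her method correctly. Without a screening test that bound does not apply. The sample size, the pharmacokinetic and pharmacodynamic endpoints and the analysis are untouched.

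**What to change.** Replace the closing sentence of the Appendix 6 paragraph on contraceptive users with:

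> *For these women only the Day -7 to Day -4 test is waived. A negative screening test no more than 28 days before dosing and a negative pre-dose test (Day -1 or Day 0) are both required, as in Section 9.5.5.*

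Add the same rule for users to schedule footnote 4. Carry it to the copy in SAP Appendix 2 (Section 10.2.1), for consistency only. Since the replacement says required where Section 9.5.5 says sufficient, align the verb there at the same time.

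The cost is a wording change in a protocol amendment, with the ethics committee submission that Appendix 4 calls for; it could go into the next amendment. Sites would do at most one urine test per affected woman, at visits where the schedule already lists it. No analysis changes.
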